2.2 Secondary Objectives

The secondary objectives are to evaluate the efficacy of SI-6603 1.25 U for key secondary endpoints, and to demonstrate whether SI-6603 1.25 U is safe and well tolerated.

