11.7 Safety Analyses

Treatment-emergent AEs will be defined as any AEs that were recorded during or following the investigational product injection. Significant TEAEs will include TEAEs that result in study discontinuation.

The incidence and its exact 95% confidence intervals (CIs) will be calculated by treatment group for TEAEs, serious TEAEs, significant TEAEs, and Treatment-emergent Adverse Events of Special Interest (TEAESI). The incidences of TEAEs, serious TEAEs, significant TEAEs, and TEAESI will be tabulated according to system organ class and preferred term by treatment group. The incidences of TEAEs and TEAESI will be tabulated by severity or time of occurrence for each system organ class and preferred term. Treatment-related TEAEs will also be summarized separately.

If a subject has more than 1 occurrence of the same AE, he/she will be counted only once within that preferred term in the summary tables. The most severe occurrence of an AE, as well as the most extreme relationship of the AE to the study procedures and investigational product, will be indicated in cases of multiple occurrences of the same AE.

Vital signs, laboratory assessments, imaging findings, and occurrence of post-treatment lumbar surgery will be summarized by treatment group. In addition, association between imaging findings and clinical symptoms will be assessed.

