1. PURPOSE OF THE ANALYSES

The purpose of the analyses described in this document is to compare the safety and efficacy of a single intervertebral disc injection of SI-6603 to a sham injection in subjects with lumbar disc herniation (LDH).

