- Cumulative distribution of percentage change from baseline in worst leg pain and ODI will be generated, and differences between the SI-6603 and control groups in the percentages of subjects experiencing a $\geq 30\%$ and $\geq 50\%$ improvement in worst leg pain score will be compared between treatments with a difference in proportions Z test. In the case of low counts (< 5 expected in a cell), a Fisher's exact test will be used. Additionally, the difference in the percentages of responders and its 95% Wald CI will be reported. Subjects with missing values will be considered non-responders/not having improvement.
- For the analysis of the percentages of responders by composite definition, differences between the SI-6603 and control groups in the percentages of positive responders will be compared between treatments with a difference in proportions Z test. In the case of low counts (< 5 expected in a cell), a Fisher's exact test will be used. Counts and percentages of responders will be presented along with 95% confidence intervals, the difference in the percentages and its 95% Wald CI. See section [7.3.3.4](#) for the definition of composite responder.
- The number of subjects with recurrence of LDH, percentages and differences between the SI-6603 and control groups in the percentages will be reported. See section [7.3.3.5](#) for the definition of recurrence of LDH.
- Time to post-treatment surgery for LDH will be evaluated by survival analysis using Kaplan-Meier methodology and the log-rank test. Counts and percentages of subjects with post-treatment surgery will be reported as well as medians and quartiles of the time to surgery (if they are defined). Additionally, the number and percentage of subjects with post-treatment surgery for LDH will be reported and compared between treatment groups with a Fisher's exact test. The difference in the percentages of responders and its 95% Wald CI will also be reported.
- Time to post-treatment surgery for LDH will be summarized in a Kaplan-Meier plot.

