8.2 Adverse Events

All AEs will be coded using Medical Dictionary for Regulatory Activities (MedDRA) using the current version at the time coding is first initiated. TEAEs will be defined as any AEs that were recorded during or following the investigational product injection. Significant TEAEs will include TEAEs that result in study discontinuation. TEAEs of special interest will include TEAEs associated with hypersensitivity, imaging findings, leg pain, and back pain.

An overall display will show the number and percentage of subjects (with exact 95% CI) with TEAEs or treatment-related TEAEs that fall into the following categories: any TEAE; TEAE leading to death; serious TEAE; significant TEAE; TEAE associated with hypersensitivity; TEAE associated with imaging findings; TEAE associated with leg pain; TEAE associated with back pain. TEAEs related to study procedure will be summarized. In addition the number of subjects with TEAEs or treatment-related TEAEs will be summarized by the following:

Relationship to Study Drug	Severity	Time of First Occurrence (after injection)
Related AEs	Mild AEs	≤ 1 day
Not Related AEs	Moderate AEs	2 – 7 days
	Severe AEs	8 days – 13 weeks
		>13 weeks

Subjects experiencing AEs in more than one category will be counted in the most severe or most related group.

Detailed listings of all AEs will include severity and relationship to treatment, as well as action taken, subject outcome, and whether the AE is diagnosed or suspected COVID-19. Separate listings will be provided of subjects who experience serious TEAEs, significant TEAEs, and special interest TEAEs. Additionally, any information recorded for AEs of diagnosed or suspected COVID-19 regarding descriptions of signs/symptoms, treatments, diagnostic test results, and the resolution will be presented in a listing.

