8.2.1 Treatment-Emergent Adverse Events by System Organ Class and Preferred Term

The total number of TEAEs and the number and percentage of subjects with events will be presented by system organ class (SOC) and preferred term (PT). Subjects are counted once in each SOC and PT. Percentages will be based on the total number of treated subjects in the treatment group. SOC will be listed in the Internationally Agreed Order (found in MedDRA Data Retrieval and Presentation: Points to Consider, Release 3.2) and PTs within a SOC will be listed alphabetically.

This will be repeated for treatment-related AEs.

8.2.2 Treatment-Emergent Adverse Events by System Organ Class, Preferred Term, and Relationship/Severity

The total number of TEAEs and the number and percentage of subjects with events will be presented by SOC and PT as described above by relationship to study drug (related, not related). At each level (SOC, PT, overall), subjects will be counted as related if they have any TEAE within that level that was deemed related.

Likewise, this presentation will be repeated by severity. Subjects will be counted at the highest severity that they experience with a given level of summarization (SOC, PT, overall).

Additionally, TEAEs related to the study procedure will be displayed as above as well as broken down by severity.

8.2.3 Serious AEs, AEs leading to death, Special Interest and Significant Treatment-Emergent Adverse Events by System Organ Class and Preferred Term

The total number of TEAEs and the number and percentage of subjects with events will be presented by SOC and PT as described above for serious AEs, TEAEs leading to death, special interest TEAEs, and significant TEAEs.

TEAEs of special interest will include TEAEs associated with hypersensitivity, imaging findings, leg pain, and back pain; significant TEAEs will include TEAEs that result in study discontinuation. Specific PTs related to each of the special interest groupings will be described in the define file for the datasets.

The number of TEAEs of special interest and percentage of subjects with events will be summarized by severity and time of occurrence. Time of first occurrence will be based on time from injection and will include the following categories: ≤ 1 day; 2 – 7 days; 8 days to 13 weeks; > 13 weeks.

All the above will be repeated for treatment-related AEs only.

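### The SAP sets out to compare safety with sham, but prespecifies no between-arm difference or interval for adverse event categories, imaging findings or the safety surgery categories

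*Protocol*

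**What the plan says.** SAP section 1 describes the purpose as "to compare the safety and efficacy of a single intervertebral disc injection of SI-6603 to a sham injection". The secondary safety objective in protocol section 2.2 is "to demonstrate whether SI-6603 1.25 U is safe and well tolerated" and names no comparator.

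The safety analyses are as follows.

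- **Overall adverse event categories.** Protocol 11.7: "The incidence and its exact 95% confidence intervals (CIs) will be calculated by treatment group for TEAEs, serious TEAEs, significant TEAEs", and likewise for events of special interest. SAP 8.2: "An overall display will show the number and percentage of subjects (with exact 95% CI) with TEAEs or treatment-related TEAEs" in each listed category.
- **Tables by organ class and term.** SAP 8.2.1: "The total number of TEAEs and the number and percentage of subjects with events will be presented by system organ class (SOC) and preferred term". No interval is named.
- **Imaging findings** (SAP 8.3.3). Counts and percentages by arm at screening, Week 13 and Week 52, with no interval.
- **Safety surgery** (SAP 8.3.4: any, for LDH at a non-target level, and not for LDH). Counts and percentages by arm, with no interval.
- **Imaging findings against symptoms** (SAP 9). Descriptive by arm.

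Binary outcomes classed as efficacy in SAP 7.3.3.3 are treated differently. Neurologic status, PGIC and CGIC response, pain response, composite response and surgery for LDH all get a between-arm difference with a 95% interval. The surgery entry reads: "The difference in the percentages of responders and its 95% Wald CI will also be reported".

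**The concern.** The sham arm is there so that events due to the disease or the procedure can be separated from events due to the product. Protocol 1.2.1.2 says that back pain was the most frequent treatment-related event in earlier studies and that the primary disease probably influences it. Section 1.2.1.5 says that procedural events can also follow sham. For harms of this kind, the useful quantity is the excess over sham together with its uncertainty.

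The plan supplies the two percentages and, in the overall adverse event display only, an interval around each. It does not supply an interval for the excess. A reader left with two one-arm intervals may compare them by eye and take overlap as no difference. The plan reports the contrast for benefits but not for harms. If it is not fixed in advance, the choice of which harms to contrast, and by what method, falls after unblinding.

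**Working it through.** **The plan's own figure.** Protocol 11.8.6 and SAP 2.6 give a 12 mm difference, SD 30 mm, 90% power, two-sided 5% and 15% dropout.

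- n per arm = 2 × (1.96 + 1.2816)² × 30² / 12² = 131.3, so 132.
- 132 / 0.85 = 155.3, so 156 per arm or 312 in total, against 320 planned. The figure reproduces.
- It concerns leg pain. Neither document states power or precision for any harm.

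**Inputs for the safety check.** 160 per arm, as planned. The documents give no adverse event rates by arm, so every rate below is an assumption. Each row doubles the sham rate.

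**Formulas.**

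- Planned one-arm interval (exact, Clopper-Pearson): lower limit is the 2.5% point of Beta(x, n − x + 1); upper limit is the 97.5% point of Beta(x + 1, n − x).
- Difference d = p₁ − p₂, with p₁ for SI-6603 and p₂ for sham.
- Newcombe limits, using each arm's Wilson limits (l, u): d − √[(p₁ − l₁)² + (u₂ − p₂)²] and d + √[(u₁ − p₁)² + (p₂ − l₂)²].

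**Worked case, 32/160 v 16/160.** The Wilson limits are 14.54-26.87% and 6.25-15.63%.

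- Lower: 10.0 − √(5.46² + 5.63²) = 10.0 − 7.84 = 2.2.
- Upper: 10.0 + √(6.87² + 3.75²) = 10.0 + 7.83 = 17.8.
- The exact intervals are 14.1-27.0% and 5.8-15.7%, which overlap.

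| Sham v SI-6603 | Exact CI, sham (%) | Exact CI, SI-6603 (%) | Overlap | Difference, points (Newcombe 95% CI) |
|---|---|---|---|---|
| 2 v 4 (1.25% v 2.5%) | 0.2-4.4 | 0.7-6.3 | yes | +1.25 (−2.3 to 5.1) |
| 4 v 8 (2.5% v 5%) | 0.7-6.3 | 2.2-9.6 | yes | +2.5 (−2.0 to 7.3) |
| 8 v 16 (5% v 10%) | 2.2-9.6 | 5.8-15.7 | yes | +5.0 (−0.9 to 11.1) |
| 12 v 24 (7.5% v 15%) | 3.9-12.7 | 9.9-21.5 | yes | +7.5 (0.5 to 14.6) |
| 16 v 32 (10% v 20%) | 5.8-15.7 | 14.1-27.0 | yes | +10.0 (2.2 to 17.8) |
| 20 v 40 (12.5% v 25%) | 7.8-18.6 | 18.5-32.4 | yes | +12.5 (4.0 to 20.9) |
| 24 v 48 (15% v 30%) | 9.9-21.5 | 23.0-37.7 | no | +15.0 (5.9 to 23.9) |

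**Why the two displays disagree.** For one-arm intervals to separate, the difference must exceed the sum of the two facing half-widths. At 20% v 10% that sum is (20.0 − 14.1) + (15.7 − 10.0) = 11.6, more than the 10.0 observed. The uncertainty of a difference combines them as a root sum of squares: √(5.9² + 5.7²) = 8.2, less than 10.0.

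**Reading the table.** The displays give opposite impressions in the 7.5%, 10% and 12.5% rows. In the rarer rows both are inconclusive, but only the difference interval states how large an excess remains possible (up to 11.1 points at 5% v 10%). At 15% v 30% they agree.

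**The case against.** Several points on the other side stand.

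- A reader might infer that the plan cannot compare safety at all. The documents do not support that. Results are shown by arm, and the excess follows by subtraction. Only its interval is missing.
- A reader might take the secondary objective to be comparative. Protocol 2.2 and SAP 2.1 name no comparator there. The comparative wording is in SAP section 1.
- No section says that harm will be judged by whether intervals overlap. The table shows what an informal reading would do, not a rule in the plan.
- A reader might infer that rare harms have no upper bound on the excess. They do, since the excess cannot be larger than the SI-6603 risk. With 0/160 the planned exact upper limit is 1 − 0.025^(1/160) = 2.28%, and the Newcombe limit for 0/160 v 0/160 is about the same at +2.3 points.
- Related outcomes already have between-arm analyses as efficacy endpoints in SAP 7.3.3.3: leg and back pain scores, disc volume, neurologic status, and surgery for LDH at the injected level. They reduce the gap but do not give the excess incidence of adverse events or imaging findings.
- Protocol 1.2.1.3 reports imaging changes after SI-6603 without a comparator rate, so a sham background for those findings is not established here.

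Describing safety without tests is a legitimate choice, and the intervals could be computed later from the planned tables. That makes this an improvement in reporting. It does not remove the benefit of fixing the contrast, method and categories before unblinding.

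**Conclusion.** The gap is confirmed but modest. Neither document prespecifies a between-arm difference or interval for adverse event categories, imaging findings or the safety surgery categories, although SAP section 1 sets out to compare safety with sham. The interval that is planned, in the overall adverse event display, does not address that comparison.

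The size depends on assumed event rates and 160 per arm. Among the doublings checked, overlapping exact intervals accompany a difference interval that excludes zero at sham rates of about 7.5% to 12.5%. It would be wrong to conclude that any doubling of a harm is hidden: at 15% v 30% the planned display already shows it. Nor would the change detect a doubling of a rare harm, since from 5% v 10% downward the difference interval also includes zero. What it adds there is a stated range for the excess. No data are lost and the efficacy tests are unaffected. This is a cheap improvement, not a fault that threatens the trial's conclusions.

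**What to change.** In protocol 11.7 and SAP 8.2, 8.3.3 and 8.3.4, before unblinding, add the difference in percentage (SI-6603 minus sham) with a 95% Newcombe or Miettinen-Nurminen interval for:

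- any, serious and significant treatment-emergent events, and each special-interest category in the SAP 8.2 overall display;
- the four imaging findings at Weeks 13 and 52;
- the three surgery categories in SAP 8.3.4, on the same denominator as the planned percentages.

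Keep the per-arm exact intervals. Label the differences descriptive and unadjusted, without p-values. The Wald interval used in SAP 7.3.3.3 is unsuitable for sparse harms: with 0/160 in both arms its standard error is zero and it collapses to a point.

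The cost is a few lines of text and routine programming, with no new data. The downside is the number of unadjusted intervals: 7 event categories + 4 × 2 imaging + 3 surgery = 18, or 25 if the 7 event categories are repeated for treatment-related events. That is a few dozen at most, so some will exclude zero by chance, and the label should say so.

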11.8 General Considerations

11.8.1 Data Handling of Worst Leg Pain

The mean worst leg pain score from 7 consecutive days prior to each visit (the day of the visit will not be included) will be used as the worst leg pain score for each time point, after excluding the worst leg pain score on any of the following days:

- Days after prohibited concomitant therapies of lumbar operation, lumbar percutaneous nucleotomy, or lumbar intradiscal therapies occurred, and
- Days before the previous visit (for example, the Week 2 visit may fall just 5 days after Week 1; thus, the days prior to the Week 1 visit will not be considered as eligible for inclusion in the 7-day Week 2 average).

In addition, if less than 3 days of worst leg pain scores are available of the 7 consecutive days prior to a visit, the worst leg pain score will be handled as missing at the time point.

For the separate analysis of the weekly pain scores throughout the study, an average of the scores every 7 days will be calculated regardless of the visit date.

11.8.2 Visit Window and Unscheduled Assessments

All data collected during follow-up will be displayed and analyzed according to the actual visit date in the eCRF. Assessments taken outside of protocol-allowable windows will be displayed according to the eCRF assessment recorded by the investigator. Unscheduled assessments (laboratory data or vital signs associated with non-protocol clinical visits or obtained in investigating or managing AEs) will be included in listings but not summaries of the data.

11.8.3 Significance Level and Confidence Coefficient

A two-sided 5% significance level for any hypothesis testing will be used, and the methodology for the adjustment of multiplicity is described in Section [11.8.5](#). A two-sided 95% confidence coefficient will be used for interval estimation unless otherwise specified.

11.8.4 Missing Data

For the efficacy analyses based on repeated-measures models of continuous endpoints, missing data will be implicitly handled via a mixed-effect model, without explicit imputation. Inferences based on this approach are unbiased under the assumption of missing at random, which is a weaker and more generally true assumption than missing completely at random. For the primary efficacy analysis, sensitivity analysis based on multiple imputation methods that changes imputation methods by missing pattern such as discontinuations due to AEs, lack of efficacy, and other will be performed for the mITT population.

For the analysis of percentages of positive responders by composite definition, subjects who discontinue the study because of AEs related to LDH or lack of efficacy and subsequently have missing efficacy data will be classified as non-responders.

No replacement of any missing data will be made for the safety analyses.

11.8.5 Adjustment for Multiplicity

To control family-wise error rate for multiple tests of the primary and key secondary endpoints, the following Holm-based testing algorithm will be used.

- The treatment effect on the primary endpoint will be evaluated at $\alpha = 0.05$.
- If the effect on the primary endpoint is significant, the treatment effect on the key secondary endpoints of herniation volume at Week 13 and worst leg pain score at Week 52 will be evaluated using the truncated Holm test at $\alpha = 0.05$. The truncation parameter will be set to 0.8.⁽¹⁴⁾
- If the effect on the key secondary endpoint of herniation volume at Week 13 is significant and/or the effect on the key secondary endpoint of worst leg pain score at

Week 52 is significant, the effect on the key secondary endpoint of ODI at Week 13 will be evaluated at a level that depends on the number of significant endpoints in the preceding step. If the key secondary endpoints of herniation volume at Week 13 and worst leg pain score at Week 52 are both significant, this level will be given by $\alpha = 0.05$; if only one of the two endpoints is significant, this level will be given by $\alpha = 0.005$.

11.8.6 Sample Size Determination

It is planned to enroll approximately 320 subjects, 160 in the SI-6603 group and 160 in the control group.

Sample size estimation is based on using the mean difference in the worst leg pain score change from baseline in the primary efficacy analysis. The following assumptions were made to compute the sample size:

- The 2-sample t-test comparing the group means of the change from baseline was used. (The 2-sample t-test approximates the test of the null hypothesis based on the repeated measures model that will be used in the primary efficacy analysis.)
- Treatment difference between SI-6603 and control groups of 12 mm
- Common standard deviation (SD) of 30 mm
- Dropout rate of 15%
- Power of 90%
- Two-sided significance level of 5%

12 ETHICAL CONSIDERATION

12.1 Good Clinical Practice Compliance

The procedures set out in this study protocol are designed to ensure that the sponsor, investigators, and other study participants abide by the principles of the Good Clinical Practice (GCP) guidelines of the International Conference for Harmonisation (ICH). The study also will be carried out in keeping with local legal requirements.

12.2 Institutional Review Board or Independent Ethics Committee Approval

If a significant safety issue is identified, either from an individual case report or review of aggregate data, then the sponsor will issue prompt notification to all parties, including regulatory authorities, investigators, and IRB(s). A significant safety issue is one that has a significant impact on the course of the clinical study or program (including the potential for

suspension of the development program or amendments to protocols) or warrants an immediate update of the ICF.

12.3 Data Protection

All study findings and documents will be regarded as confidential. The investigator and members of his/her research team must not disclose such information without prior written approval from the sponsor.

The anonymity of participating subjects must be maintained. Subjects will be identified on the eCRF and other documents submitted by their subject number, initials, and/or birth date, not by name. Documents not to be submitted that identify the subject (e.g., the signed ICF) must be maintained in confidence by the investigator.

12.4 Premature Termination of the Study

If the Investigator, the Sponsor, or the Medical Monitor becomes aware of conditions or events that suggest a possible hazard to subjects if the study continues, the study may be terminated after appropriate consultation between the relevant parties. The study may also be terminated early at the Sponsor's discretion in the absence of such a finding.

Conditions that may warrant termination include, but are not limited to:

- The discovery of an unexpected (e.g. AE other than AEs listed in Table 6.1. in the current edition of the investigator brochure), significant, or unacceptable risk to the subjects enrolled in the study
- The occurrence of an AE considered at least possibly related to SI-6603, as noted below:
 - a. Significant neurologic deficit; for example, progressive weakness or sudden loss of muscle strength, bowel or bladder dysfunction, or other signs and symptoms of cauda equine / conus medullaris involvement;
 - b. Abnormal X-ray findings of instability, defined as vertebral body angle formed by flexion of $\geq 5^\circ$ or vertebral body translation of ≥ 3 mm; or
 - c. Abnormal X-ray or MRI findings which subjects exhibit correlating clinical symptoms posing safety concerns, leads the investigator to judge it necessary for the subject to have surgical intervention
- Failure to enroll subjects at an acceptable rate
- A decision on the part of the sponsor to suspend or discontinue development of the drug

